10.1.3.2 Days 2-7, 9-14, 16-20

- BGB324 and erlotinib (Arms A, B, and C) will be self-administered orally on an empty stomach by the patient at home.

10.1.4 Cycles ≥3-C17

All AEs and concomitant medication use will be recorded throughout each cycle.

10.1.4.1 Day 1

- Performance status assessment.
- Symptom-directed physical examination.
- Vital signs.
- Serial 12-lead ECGs, in triplicate.
- Urine pregnancy test at 3 month intervals.
- Clinical chemistry, hematology, urinalysis, coagulation (+/- 3 days).
- Blood sampling for PK.
 - PK sampling in Arm B will be for BGB324 only- and will continue to Cycle 3, Day 1 - see Table 6
- Echocardiogram or MUGA scan (Cycle 4 only).
- BGB324 administration orally, on an empty stomach.
- Erlotinib administration (Arms A, B, and C) orally, on an empty stomach.
- Drug accountability.

10.1.4.2 Days 2-20

- BGB324 and erlotinib (Arms A, B, and C) will be self-administered orally, on an empty stomach, by the patient at home.

10.1.5 End-of-study visit

The following assessments will then be carried out at the EOS visit (28 days after the last dose of study drug) for every patient enrolled into the study.

- Performance status assessment.
- Physical examination.

- Vital signs.
- Serial 12-lead ECGs, in triplicate
- MUGA/ECHO.
- Serum pregnancy test.
- Clinical chemistry, hematology, coagulation and urinalysis.
- Blood sampling for PK
 - PK sampling in Arm B will be for BGB324 only - see Table 6.
- Disease assessment (if not performed within previous 28 days).
- Drug accountability.
- AEs assessment.
- Concomitant medications assessment.

10.1.6 Assessments at disease progression

The following assessments are required at disease progression

- Tissue collection for PD (in consenting patients) (Arms A, B, and C).
- Blood collection for PD (Arms A, B, and C).
- CT scan and RECIST evaluation (as per local standards).

10.1.7 Visit schedule after 12 months of treatment

Patients who remain on BGB324 for 12 months or more will be able to reduce the frequency and number of assessments required at each visit.

Patients will return to clinic every 6 weeks (every 2 cycles). The following assessments will be undertaken:

- Symptom-directed physical examination (every 3 months).
- Serial 12-lead ECGs, in triplicate.
- Clinical chemistry, hematology, urinalysis (every 3 months).
- Drug accountability.
- AE and concomitant medication reporting.
- Pregnancy test as applicable (every 3 months).

10.1.8 Visit schedule while on corticosteroids

Patients receiving BGB324 who require the support of prednisolone (or equivalent) at 10mg to 40mg daily should be monitored at weekly intervals whilst receiving steroid treatment until the steroid dose is 10mg or less daily or is stopped.

Patients will be requested to return weekly at which time the following assessments will be undertaken:

- Physical examination
- Vital signs
- Clinical chemistry, hematology
- AE reporting/concomitant medication reporting

Patients who require daily steroids of more than 40mg prednisolone (or equivalent) should interrupt BGB324 until the steroid dose is 40mg or less daily.

Steroid restrictions do not apply to topical/ inhaled/ eye or nasal drops.

If required, additional advice on the concomitant use of steroids with BGB324 should be obtained from the BerGenBio Medical Monitor

Patients who are already attending weekly visits for C1 and C2 do not require additional visits.

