--	--

	
inhibitors which must be completed 1 week prior to commencing treatment with BGB324. There is no requirement to discontinue ongoing treatment with erlotinib.
 
26. Treatment with other non-cytotoxic agents for NSCLC in the 10 days or 4 half-lives, prior to the first dose of BGB324 (Cycle 1, Day 1) whichever is shorter.
 
27. Prior biological therapies in the 4 weeks (or 5 half-lives, whichever is shorter) before the first dose of BGB324 (Cycle 1, Day 1). Note prior treatment with an alternative EGFR inhibitor and/or PD-1 blockade is permitted.

TREATMENTS AND INTERVENTIONS	
Patient eligibility for the study, including assessment of EGFR mutation/T790M status in Arm B, and disease status according RECIST Version 1.1 will be performed within 28 days prior to the first dose of BGB324. The 28-day screening window may be extended to confirm T790M status, however all other assessments including scans will be conducted in the 28-day screening window. Patients who have previously been treated with a T790M inhibitor (i.e., osimertinib) and who subsequently progressed and fulfil all other eligibility criteria will not require T790M testing.
 
The treatment period will consist of continuous 21-day treatment cycles. Patients will be monitored through daily clinic visits on Day 1 to Day 4, Days 8, 9, and 15 in Cycle 1 (and Day -1 in Arms A and B) and weekly during Cycle 2. Beginning with Cycle 3, patients will have a clinic visit on Day 1 of each cycle. Patients who remain on treatment for 12 months will need to return for a clinic visit every 2 cycles (i.e. 6 weekly).
 
Patients receiving BGB324 who require the support of prednisolone (or equivalent) at 10mg to 40 mg daily should be monitored at weekly intervals whilst receiving treatment.
 
Disease assessment will be performed at the end of every 2 cycles or to confirm disease progression. The frequency of scans may be extended to the end of every 3 cycles after 12 weeks (4 cycles) and every 4 cycles after 24 weeks (8 cycles). Patients who remain on treatment for 12 months or longer may have their scans extended to a frequency of 6 months, unless disease progression is suspected in which case a scan should be conducted at an earlier time point.
 
The end of study (EOS) visit will occur 28 days after the last dose of study drug (including study withdrawal).

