8.8 Treatment

Eligible patients will visit the study site to receive study drug and protocol-specified procedures according to Section 10.1.2 to Section 10.1.4 and Table 5. The treatment period will consist of continuous 21-day treatment cycles.

All patients will be carefully monitored throughout Day 1 to Day 4 in Cycle 1 and will attend the clinic on Cycle 1, Day 8, Cycle 1, Day 9 and Cycle 1, Day 15 (and Day -1 in Arm A).

Patients will attend the clinic once per week (on Cycle 2, Day 1, Cycle 2, Day 8 and Cycle 2, Day 15) during Cycle 2 and then once per cycle (on Day 1) thereafter up to 12 months of

treatment (Cycle 17). Patients who remain on study after 12 months will attend the clinic every 2 cycles (6 weekly).

Patients who do not receive loading doses as assigned but are considered suitable for daily dose treatment should attend the clinic for additional ECG assessments. Twice weekly triplicate ECGs should be conducted during Cycle 1, Day 8 – Day 15 and Cycle 1, Day 15 -Day 21.

Additional visits will be scheduled for disease assessment at the end of every 2 cycles (6 weeks) cycles. The frequency of scans may be extended to the end of every 3 cycles after 12 weeks (4 cycles) and every 4 cycles after 24 weeks (8 cycles). Patients who remain on treatment for 12 months or longer may have their scans extended to a frequency of 6 months unless disease progression is suspected in which case a scan should be conducted at an earlier time point.

Patients will continue to receive BGB324 (in combination with erlotinib or as a single agent) for as long as, in the opinion of the Investigator, they continue to derive clinical benefit or until disease progression, unacceptable toxicity, death or withdrawal of consent.

In the event of erlotinib-related toxicities in Arms A, B, and C, patients may be allowed to continue receiving BGB324 as a single agent until disease progression unless unacceptable toxicity, death or withdrawal of consent. Patients who stop BGB324 treatment will be withdrawn from the study.

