- u. Patients in Arm B must have EGFR T790M status confirmed during screening – Patients who have progressed on osimertinib and have previously progressed on an approved EGFR inhibitor i.e. afatinib, gefitinib) will not require additional T790M testing. T790M testing may be confirmed by blood test or biopsy. Samples collected and analyzed according to local procedures. The screening window of 28 days may be extended to allow for confirmation of T790M status.
- v. Patients who do not receive their assigned loading doses and continue to receive daily dose BGB324 should attend the clinic for additional ECG assessments between C1 D8 and D15 and between C1 D15 and the end of Cycle 1.
- w. Patients who remain on study post C17 will have a reduced visit schedule and will return to clinic every 2 cycles (+/-7 days)
- x. Patients receiving BGB324 who require daily steroids at doses of 10mg to 40mg (prednisolone equivalent) should be monitored at weekly intervals until the steroid dose level is less than 10mg: Assessment should include physical exam, vital signs, hematology, chemistry.

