11.3.1.4 BGB324 dose modification for steroids doses over 40mg daily (prednisolone equivalent)

If a patient requires prednisolone (or equivalent) at daily doses above 40mg then BGB324 should be interrupted until the steroid dose is equivalent to or less than 40mg daily, at which time weekly monitoring will be undertaken until the steroid dose is equivalent or less than 10mg (Section 10.1.8)

For those patients who experience a BGB324 dose delay of ≥7 days, the BGB324 loading dose assigned should be repeated. If the patient was unable to tolerate the loading dose in Cycle 1 the repeat loading dose can be omitted. The requirement to reintroduce the loading dose should be discussed with the Medical Monitor.

Steroid restrictions do not apply to topical/ inhaled/ eye or nasal drops. If required, additional advice on the concomitant use of steroids with BGB324 should be obtained from the BerGenBio Medical Monitor.

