11.5 Concomitant Medication and Procedures

All prescription, non-prescription, or over-the-counter medications, including herbal remedies, taken by the patient at entry and during the study must be clearly documented in the eCRF.

The patients must be instructed that no additional medication will be allowed without the prior consent of the Investigator. Any medication considered necessary for the patient's safety and well-being may be given at the discretion of the Investigator.

Hematopoietic growth factors may be administered for the treatment of AEs such as neutropenic infections but should not be used to maintain the dose intensity of BGB324 in the Run-in Cohort or Arm A.

Patients who have evidence of treatment benefit after ≥ 1 cycle (21 days) of treatment in Arms B or C may receive hematopoietic growth factors to maintain BGB324 dosing.

Concurrent treatment with any agent known to cause Torsade de Points is an exclusion criterion for the study. A comprehensive list of these prohibited medications is provided in Appendix 3.

Anti-diarrheal medications (e.g. loperamide) may be administered according to standard practice for the management of diarrhea. Patients must be provided with anti-diarrheal medications to take home, which may be used if required.

Patients being treated with antacid, histamine receptor 2 inhibitors or proton pump inhibitors on study entry will be excluded. The Investigator may initiate rescue treatment with these medications during the study, providing they are taken in the evening.

Patients receiving BGB324 who require the support of prednisolone (or equivalent) at 10mg to 40mg daily should be monitored at weekly intervals whilst receiving treatment. If a patient requires prednisolone (or equivalent) at daily doses above 40mg then BGB324 should be interrupted until the steroid dose is equivalent or less than 40mg daily, at which time weekly monitoring will be undertaken until the steroid dose is equivalent or less than 10mg.

Steroid restrictions do not apply to topical/ inhaled/ eye or nasal drops. If required, additional advice on the concomitant use of steroids with BGB324 should be obtained from the BerGenBio Medical Monitor.

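### Two safety thresholds have narrow boundary errors: weekly steroid monitoring is both required and ended at exactly 10 mg, and Table 8 gives a mean QTcF of 501 ms no band

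*Protocol*

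**What the plan says.** **Steroids.** Protocol 10.1.8 places patients on 10 to 40 mg prednisolone (or equivalent) daily under weekly monitoring and, in the same sentence, continues it "until the steroid dose is 10mg or less daily or is stopped". The synopsis has the same starting range: "prednisolone (or equivalent) at 10mg to 40 mg daily should be monitored at weekly intervals whilst receiving treatment". Section 11.5, copied into SAP 4.4.2, also starts at 10 mg. It adds that BGB324 is interrupted above 40 mg and that, once the dose is back to 40 mg or lower, the patient resumes under supervision, "at which time weekly monitoring will be undertaken until the steroid dose is equivalent or less than 10mg". Section 11.3.1.4 uses the same stop and refers back to 10.1.8. Footnote x to Protocol Table 5, repeated under SAP Table 2, says instead that these patients "should be monitored at weekly intervals until the steroid dose level is less than 10mg".

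**Background visits.** Section 10.1.8 closes with: "Patients who are already attending weekly visits for C1 and C2 do not require additional visits". Under section 8.8, patients attend weekly "during Cycle 2 and then once per cycle (on Day 1) thereafter up to 12 months of" treatment. Section 10.1.7 then moves them to one visit every two cycles, that is, every 6 weeks.

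**QTcF.** Table 8 in Protocol 11.3.1.3 prints Grade 1 as 451-480 ms, Grade 2 as 481-500 ms and Grade 3 or higher as strictly greater than 501 ms. Its notes apply these bands to the mean of the triplicate readings. Neither the notes nor section 10.2.4 says how that mean is rounded.

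**The concern.** Both rules are in current text, not only in the summary of changes, and both govern patients still being treated in Arms B and C.

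For steroids, the ambiguous dose is the very one the protocol names as its threshold. Two sites with the same patient at 10 mg could follow different schedules, and each could cite the protocol. No order of precedence is given between the text sections and the footnote.

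For QTcF, the unassigned value lies between rows that call for different actions. At a first occurrence, the Grade 2 row keeps the patient on BGB324 with weekly ECGs and reduces the dose by 100 mg only if QTcF has not returned to Grade 1 or lower within 14 days. The Grade 3 row interrupts at once. It then reduces by 100 mg if QTcF recovers, or discontinues if it does not recover or no lower dose exists. At a second occurrence, the Grade 3 row is permanent discontinuation.

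**Working it through.** There is no planned figure to reproduce. The check is to write the printed thresholds as inequalities and see which values satisfy two contradictory rules, or none.

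**Steroid rule.** Let d be the daily prednisolone-equivalent dose in mg.

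- Start: 10 ≤ d ≤ 40 (10.1.8, synopsis, 11.5, SAP 4.4.2).
- Stop, form A: d ≤ 10 (10.1.8, 11.3.1.4, 11.5, SAP 4.4.2). I read the slightly garbled wording in 11.3.1.4, 11.5 and SAP 4.4.2 as equal to or less than. That agrees with 10.1.8 and with how the same sections treat the 40 mg limit.
- Stop, form B: d < 10 (footnote x in both documents).

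| d (mg) | Start met | Stop A met | Stop B met |
|---|---|---|---|
| 9 | no | yes | yes |
| 10 | yes | yes | no |
| 10.5 | yes | no | no |
| 40 | yes | no | no |

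Only d = 10 is both required and released under form A. Under form B no dose is. Footnote x does not clearly settle the matter, because its marker is printed against weeks 1 to 6 only, when visits are weekly anyway.

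**Visits that depend on the reading.**

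- Cycles 1 and 2: none, since visits are already weekly.
- Cycles 3 to 17: 15 cycles × 3 weeks = 45 weekly visits, against 15 scheduled Day 1 visits. 45 − 15 = 30, and 30/45 = 2 of 3. The 30 is a ceiling for a patient held at exactly 10 mg throughout.
- After 12 months: 6 weekly visits against 1 per 6 weeks, so 5 of 6. This counts attendance only. The routine visit in 10.1.7 lists examination, chemistry and hematology only every 3 months and lists no vital signs. It therefore does not supply the set of checks in 10.1.8, and the gap in checks is wider than 5 of 6.

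**QTcF bands.** In whole milliseconds, the printed bands are 451-480, 481-500 and 502 upward. The only whole number from 451 upward with no band is 501.

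The mean of three whole-ms readings moves in thirds. The means that fall in no band are:

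- Grade 1/2 boundary: 1441/3 = 480.33 and 1442/3 = 480.67.
- Grade 2/3 boundary: 1501/3 = 500.33, 1502/3 = 500.67 and 1503/3 = 501.00.

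The lower gap separates no dose modification from weekly ECGs with a possible 100 mg reduction.

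**Checking the two repairs.** With contiguous bands (>450 to 480, >480 to 500, >500), each of the five values falls in exactly one band: 480.33 and 480.67 in Grade 2, the other three in Grade 3 or higher. With rounding to whole ms and Grade 3 or higher as ≥501, they become 480 (Grade 1), 481 (Grade 2), 500 (Grade 2), 501 and 501 (Grade 3 or higher). Both repairs close the table, but they grade 480.33 and 500.33 differently, so the sponsor must choose one.

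**The case against.** The best case for leaving the text alone is that both errors are very narrow and neither leaves the site without guidance.

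- Table 8 is entered by grade, CTCAE 4.03 is the protocol's severity scale (13.3.1, Appendix 4), and the actions are recommendations. The notes ask that patients considered for reduction or discontinuation be discussed with the Medical Monitor. Even on the Grade 2 reading, weekly ECGs follow, so a further rise would reach the Grade 3 row.
- For steroids, 10.1.8, 11.3.1.4 and 11.5 all offer Medical Monitor advice. The 40 mg interruption limit is consistent throughout.

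This stands as far as it goes, and it keeps the point minor. It does not make the text right. The CTCAE limits are not printed in the protocol, and a table that decides whether to interrupt a drug should not depend on an outside lookup at its most important boundary. The offer of Medical Monitor advice on steroids applies only if advice is sought. A site that reads 10.1.8 as releasing the patient would see no reason to ask.

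A misread character (> for ≥) in the Grade 3 limit cannot be excluded. It is unlikely, because the same row label prints ≥ correctly before the grade.

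The mouse findings in 6.1.5 might suggest that 10 mg is itself hazardous. The documents do not support that: the steroid dose there is described as 20-fold above a typical high clinical dose, and the BGB324 dose as 6-fold above the maximum human exposure.

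**Conclusion.** Both boundary errors are real and minor. One dose, exactly 10 mg, is both in and out of weekly monitoring. One whole-ms QTcF value, 501, has no band, and without a rounding rule the means 500.33, 500.67, 480.33 and 480.67 have none either.

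The steroid consequence begins in Cycle 3, at 2 of 3 weekly visits up to Cycle 17, and widens after 12 months. The documents do not say how many patients would be held at 10 mg, so the total burden cannot be sized.

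Three further inferences should be resisted.

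- That patients at 10 mg go unmonitored: they keep their routine visits, less often.
- That the two QTcF rows differ by at most 14 daily doses: the Grade 3 row can end in discontinuation, since reduction below 100 mg is impossible and Table 4 includes 100 mg daily doses. All later treatment may be at stake.
- That the trial's conclusions are affected: no endpoint, population, sample size, alpha or power depends on either rule, and the SAP's QTcF summary is by CTCAE grade.

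**What to change.** 1. Make the stop *less than 10 mg daily* in Protocol 10.1.8, 11.3.1.4 and 11.5 and in SAP 4.4.2. This matches the 10 mg start and the wording already in footnote x.
2. In Table 8, do one of the following:
   - print contiguous bands: Grade 1 >450 to 480 ms, Grade 2 >480 to 500 ms, Grade 3 or higher >500 ms; or
   - keep whole-ms bands, print Grade 3 or higher as ≥501 ms, and state that the triplicate mean is rounded to a whole millisecond before grading.

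Changing only the top band to >500 ms is not enough, because it leaves 480.33 and 480.67 ms without a band.

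The cost is a few words in an amendment and in the SAP. Patients held at exactly 10 mg would attend weekly: 2 extra visits per cycle in Cycles 3 to 17, and 5 extra per 6 weeks after 12 months. The 10 mg start rule already requires those visits.

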10.2 Details of Study Procedures

10.2.1.1 Clinical Laboratory Assessments

The following clinical laboratory parameters will be measured at a local laboratory:

- Clinical chemistry (serum): potassium, calcium, uric acid, electrolytes, blood urea nitrogen, total protein, total bilirubin, ALT, AST, creatinine, creatine phosphokinase, alkaline phosphatase, albumin, phosphorus, glucose, magnesium plus amylase and lipase (during screening only).
- Hematology: full blood count including differential white cell count, hemoglobin, hematocrit and platelets.
- Coagulation parameters: prothrombin time and/or INR, aPPT.
- Urinalysis: Dipstick measurement of blood, nitrite, glucose, ketones, leukocytes, protein, and pH. (microscopic analysis is not required unless clinically indicated).
- EGFR T790M to be undertaken in accordance with local standard practice.

All tests will be performed at screening (and on Cycle 1, Day -1 for patients in Arm A)

Thereafter, clinical chemistry and hematology will be performed at each study visit. Coagulation will be performed on Days 1, 8, and 15 in Cycle 1, Day 1 in all subsequent cycles and the end-of-study visit.

Urinalysis will be performed on Days 1, 8, and 15 in Cycle 1 and Cycle 2, Day 1 in all subsequent cycles and the EOS visit.

10.2.2 Pregnancy test

In women of child bearing potential a serum pregnancy test should be taken at screening and Day 1 (and on Cycle 1, Day -1 for patients in Arm A unless conducted as part of screening procedures within 3 days prior to Cycle 1, Day 1) and at the EOS visit.

During the study, a urine pregnancy test should be repeated every 3 months.

Should a patient suspect that pregnancy may have occurred an unscheduled pregnancy test should be conducted. The patient must have negative tests for eligibility and continuation on the study.

10.2.3 Vital signs

Blood pressure, pulse, respiratory rate and oral temperature will be consistently recorded at all study visits (with the exception of visits performed for disease assessment).

10.2.4 Triplicate 12-lead ECG

Triplicate 12-lead ECGs, at least 5 minutes apart, will be performed after resting for ≥ 10 minutes in supine position during screening and pre-dose on Day -1 (Arms A and B) then Day 1, 2, 3, 4, 8, 9, and 15 in Cycle 1, pre-dose on Days 1, 8, and 15 in Cycle 2, pre-dose on Day 1 in Cycle 3 onwards, and at the EOS visit.

Patients who do not receive loading doses as assigned but are considered suitable for daily dose treatment should attend the clinic for additional ECG assessments. Twice weekly ECGs should be conducted during Cycle 1, Day 8 - Day 15 and Cycle 1, Day 15 – Day 21.

Continuous variables (PR interval, RR interval, QRS duration, QT and QTcF intervals) and an overall assessment will be recorded in the electronic case report form (eCRF).

QTc values recorded should be calculated as the average from the 3 traces taken.

10.2.5 Echocardiogram/MUGA

An ECG or MUGA scan will be performed at screening at 6 monthly intervals and at the EOS visit.

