- l. Blood will be collected for analysis of pharmacodynamic endpoints of Axl inhibition. The baseline sample should be collected after enrollment within 28 days before the first dose of BGB324. The on-study sample collection may be performed any time after 14 days of continuous exposure to BGB324 in Cycle 1 or in Cycle 2. The EOSEOS sample should be taken at the time of disease progression and prior to the EOS-visit.
- m. If a tissue specimen is being collected, the PD blood sample should be collected at the same visit.
- n. Disease assessment via RECIST Version 1.1.
- o. BGB324 and erlotinib (not Run-in Cohort) will be administered on an empty stomach. Both drugs will be taken with water in the morning. BGB324 should be administered in the hour following erlotinib administration and at least 2 hours before breakfast (except on those days when the patient attends the clinic). Patients should record dosing in the dosing diary provided.
- p. Disease assessment will be performed at the end of every 2 cycles (6 weeks) beginning with Cycle 2 (Day 21); the assessment may be performed up to 5 days before Day 21 (Day 17-Day 21) but attempts should be made to conduct the assessment as close to Day 21 as possible. Disease assessment may be performed prior to initiation of the next cycle, but results must be available prior to initiation of treatment and must confirm continued eligibility for next cycle. The frequency of scans may be extended to the end of every three cycles after 12 weeks (4 cycles) and every 4 cycles after 24 weeks (8 cycles). Patients who remain on study for 12months may have their scan frequency reduced to 6 monthly.

- q. For consenting patients' only (Arms A, B and C); performed any time after documentation of disease progression and prior to EOS visit. The tissue specimen should be derived from a lesion exhibiting progression.
- r. If not performed within previous 28 days.
- s. To be performed at the time of disease progression and prior to the EOS visit.
- t. Cycle 4 Day 1 and then at 6 monthly intervals and at EOS.

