10.1 Procedures at each Visit

10.1.1 Screening and enrollment

Patients must provide written informed consent before any screening procedures are performed. The screening period covers up to 28* days prior to the first dose of BGB324.

During screening, the following procedures will be performed:

- Demographics.
- Medical history.
- Cancer history and treatments (medications and surgeries).
- EGFR mutation recorded
- T790M status confirmed in the screening period (Arm B)⁴
- Performance status assessment (ECOG).
- Physical examination.
- Vital signs (including height and weight)
- Serial 12-lead ECGs, in triplicate.
- Serum pregnancy test, if applicable.
- Clinical chemistry, (including amylase and lipase), hematology, urinalysis, coagulation
- Echocardiogram or MUGA scan.
- Disease assessment.
- Review of inclusion/exclusion criteria.

Male patients and female patients of reproductive potential must agree to practice highly effective methods of contraception throughout the study and for ≥3 months after the last dose of BGB324. Highly effective methods of contraception are defined as:

- Hormonal implants, combined oral contraceptives, injectable contraceptives.
- An intrauterine device with hormone spirals.
- Tubal ligation.
- True total sexual abstinence.
- Vasectomy.

If it is not possible to use one of these highly effective methods of contraception, 2 barrier methods used simultaneously are acceptable.

The following baseline samples should be taken in the 28 days before the first dose of BGB324 after the patient has been confirmed as otherwise eligible:

- Blood collection for PD (Arms A, B, and C only).
- Tissue collection for PD (consenting patients only) (Arms A, B, and C).

Patients who meet all inclusion/exclusion criteria will be allocated a study-specific patient number.

10.1.2 Cycle 1

All AEs and concomitant medication use will be recorded throughout the cycle.

⁴ The screening period for Arm B may be extended to allow for confirmation of T790M status all other assessments are to be conducted in the 28-day screening period. Patients who have previously been treated with a T790M inhibitor (i.e., osimertinib) and who subsequently progressed will not require T790M testing.

In addition, tissue (in consenting patients) and blood will be collected for pharmacodynamic assessment at one on-study time point after 14 consecutive days of BGB324 administration either in Cycle 1 or Cycle 2 (Arms A, B, and C).

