3.1 Safety End-points

Safety and tolerability will be assessed by conducting the following safety assessments at pre-defined time-points during the study:

- Treatment emergent adverse events (TEAE)
- Physical examination
- Vital signs including blood pressure (BP), heart rate (HR)
- Electrocardiogram (ECG) or multi-gated acquisition (MUGA) scan
- 12-lead triplicate ECG
- Clinical laboratory parameters including clinical chemistry, hematology coagulation and urinalysis
- Eastern Co-operative Oncology Group (ECOG) performance status

The primary objective of Arm A is to identify the RP2D of BGB324 administered in combination with erlotinib in patients with NSCLC. This will be accomplished by evaluation of the safety and occurrence of DLTs at each dose level.

AEs will be assessed using the National Cancer Institute (NCI) Common Toxicity Criteria for Adverse Events (CTCAE) Version 4.03 criteria during the first cycle (21 days) of treatment for the purposes of establishing the dose of BGB324 that can safely be given in combination with erlotinib.

DLTs will include:

- Any non-hematological toxicity \geq Grade 3 except Grade 3 nausea, vomiting or diarrhea that resolves within 72 hours with optimal therapy;
- Grade 4 thrombocytopenia or Grade 3 thrombocytopenia with bleeding.
- Grade 4 neutropenia persisting for \geq 5 days or Grade 3 or 4 febrile neutropenia.
- Treatment discontinuation or dose reduction for $>$ 72 hours during the first cycle as a result of treatment-related toxicity.

A patient must receive all loading doses and miss no more than 3 daily doses in Cycle 1 (21 day cycle of treatment) to be considered as informative to support dose escalation, unless the inability to administer BGB324 was a result of treatment-related toxicity.

If 1 patient in a cohort experiences a DLT during Cycle 1, the cohort will be expanded to 6 patients. If 2 of 3 or 2 of 6 patients in a cohort experience DLT, no further dose-escalation will take place and the prior dose level will be nominated as the RP2D (see section 8.3.2 of the protocol).

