5.8.5 Electrocardiograms

Twelve-lead ECG triplicate will be collected the mean of the values will be analysed. In case, only one assessment is collected this value will be considered, if 2 or 3 assessments are performed the mean of available should be calculated.

The quantitative ECG assessments (PR interval (ms), RR interval (ms), QRS Duration (ms), QT interval (ms), and QTcF interval (ms)) will be summarized for actual values and change from Baseline to each visit/timepoint will be also presented.

ECG overall interpretation (normal, abnormal not clinically significant and abnormal clinically significant) will be presented as a categorical summary by treatment groups and scheduled visit.

Any post-baseline new or worsened echocardiogram findings during the safety evaluation period will be recorded as AEs and summarized in terms of AEs as described in [Section 5.8.1](#).

All echocardiogram data, including MUGA scan results will be presented in a data listing.

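### The protocol gives three different on-treatment echocardiogram/MUGA schedules for a named safety endpoint, and 10.2.5 and SAP 3.1 misname the test

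*Protocol*

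**What the plan says.** Protocol 7.5 lists echocardiogram or MUGA among the safety endpoints, separately from the 12-lead ECG. The scheduling passages are:

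- **Screening (10.1.1):** "Echocardiogram or MUGA scan". The end-of-study list in 10.1.5 also has the scan. Table 5 and 10.2.5 agree with both.
- **Table 5, note t (repeated as note t to SAP Table 2):** "Cycle 4 Day 1 and then at 6 monthly intervals and at EOS".
- **Day 1 visits of Cycles 3 to 17 (10.1.4.1):** "Echocardiogram or MUGA scan (Cycle 4 only", given in parentheses as the limit on that item.
- **Procedure section 10.2.5:** "An ECG or MUGA scan will be performed at screening at 6 monthly intervals and at the EOS visit".
- **After 12 months (10.1.7):** "Patients who remain on BGB324 for 12 months or more will be able to reduce the frequency and number of assessments required at each visit". It continues: "Patients will return to clinic every 6 weeks (every 2 cycles). The following assessments will be undertaken". The list that follows has examination, 12-lead ECG, laboratory tests, drug accountability, adverse events and concomitant medication, and pregnancy test. It has no echocardiogram or MUGA.

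On the name of the test, 10.2.5 writes ECG, which the abbreviation lists of both documents define as electrocardiogram. SAP 3.1 spells it out: "Electrocardiogram (ECG) or multi-gated acquisition (MUGA) scan". SAP 5.8 lists ECG and echocardiograms as separate items, and SAP 5.8.5 states: "All echocardiogram data, including MUGA scan results will be presented in a data listing".

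**The concern.** Safety and tolerability is the primary objective of the Run-in Cohort, Arm B and Arm C. Treatment is open-ended, and an abnormal ejection fraction excludes a patient at entry. The times at which cardiac function is checked during treatment should therefore be the same for every patient.

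Section 8.8 tells sites to follow Sections 10.1.2 to 10.1.4 and Table 5. Those two sources disagree after Cycle 4, and nothing says which governs. Section 10.2.5 gives a third schedule. A site that follows one stated passage in good faith omits scans that another passage requires. The omission depends on the source used: the visit lists drop the later scans, and 10.2.5 drops the early one.

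**Working it through.** The plan gives no count of its own to reproduce. The check is a calendar count of on-treatment scans under each source, leaving out screening and end of study, where there is no conflict.

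**Inputs from the documents.** Cycles last 21 days (8.8). The end-of-study visit is 28 days after the last dose (8.9). The schedules are as quoted above.

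**Assumptions.** Six months is 6 × 30.4375 = 182.6 days. The note t intervals run from Cycle 4 Day 1 and the 10.2.5 intervals from Day 1; neither passage states its starting point. The 10.1.7 list is read as complete. The treatment durations are illustrative, because the documents give no expected duration.

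**Dates.**
- Cycle 4 Day 1 = 3 × 21 + 1 = day 64.
- Note t: day 64; 64 + 182.6 = day 247; 64 + 365.25 = day 429.
- 10.2.5: 1 + 182.6 = day 184; 1 + 365.25 = day 366; 1 + 547.9 = day 549.
- Visit lists (10.1.4.1 and 10.1.7): day 64 only. Cycle 17 ends on day 17 × 21 = 357.

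| Time on treatment | Note t | 10.2.5 | Visit lists |
|---|---|---|---|
| 3 to 5 months | 1 (day 64) | 0 | 1 (day 64) |
| 12 months | 2 (days 64, 247) | 2 (days 184, 366) | 1 (day 64) |
| 18 months | 3 (days 64, 247, 429) | 3 (days 184, 366, 549) | 1 (day 64) |

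The 10.2.5 counts at 12 and 18 months include a scan due as treatment ends (days 366 and 549). Without it they are 1 and 2.

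**Where the conflict is direct and where it is silence.** The second note t scan, day 247, falls in Cycle 12. That is inside Cycles 3 to 17, where 10.1.4.1 restricts the scan to Cycle 4, so this is a contradiction in terms. The third, day 429, falls after Cycle 17. There the difference rests on 10.1.7 not mentioning the scan.

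**Longest interval, patient treated 18 months.** The last dose is at about day 18 × 30.4375 = 548 and end of study at about day 548 + 28 = 576. Under the visit lists the interval without a scan is 576 − 64 = 512 days, or 512 / 30.4375 = 16.8 months. Under note t no interval after Cycle 4 exceeds about 183 days.

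**Name of the test.** Two places say ECG or electrocardiogram: 10.2.5 and SAP 3.1. Protocol 7.5, 10.1.1, 10.1.4.1 and Table 5, and SAP 5.8, 5.8.5 and Table 2, say echocardiogram; protocol 10.1.5 abbreviates it to ECHO.

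**The case against.** The strongest reply is that Table 5 carries the fullest schedule, the SAP copies it, and 8.8 names it, so a site using Table 5 performs the scans. That is true, but 8.8 names 10.1.4 in the same sentence, and 10.1.4.1 restricts the scan to Cycle 4. The direction to both sources leaves the conflict in place.

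A second reply concerns 10.1.7. Its list also omits disease assessment, which 7.6 and 10.2.10 plainly continue after 12 months, so absence from the list need not mean the scan is dropped. This stands in part. The silence is ambiguous, particularly in a section that permits fewer assessments, and it needs clarifying, but it is weaker evidence than the wording of 10.1.4.1. It should also be said that the long interval without a scan does not come from 10.2.5, which itself asks for 6-monthly scans.

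Three stronger readings are tempting, and the documents do not support them:

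- **That the routine 12-lead ECG satisfies 10.2.5, leaving no cardiac-function measurement at all.** The sentence stands under a heading that names echocardiogram and MUGA, directly after a separate section on the 12-lead ECG, and SAP 3.1 lists the 12-lead ECG as its own item. This is a slip in the name of the test.
- **That pooled cardiac results would be distorted.** SAP 5.8.5 plans only a listing of these data, with new or worsened echocardiogram findings summarised as adverse events. No pooled ejection-fraction table is planned.
- **That the SAP is deficient for lacking an ejection-fraction summary.** Protocol 14.2.2 promises summary statistics for vital signs, 12-lead ECG and laboratory data, not for echocardiograms. No passage shows that a numeric ejection fraction is recorded during treatment.

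**Conclusion.** The point holds as an internal contradiction about when a named safety endpoint is measured during treatment, with a separate error in the name of the test. It is more than clerical, because following one stated passage omits scans that another requires: one scan against three at 18 months (visit lists against note t), and none against one for a patient who stops after Cycle 4 Day 1 but before 6 months (10.2.5 against the other two).

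The 12- and 18-month figures depend on the assumed starting points of the 6-month intervals, and the 18-month figure also on reading 10.1.7 as complete. The contradiction between note t and 10.1.4.1 within Cycles 3 to 17 does not depend on 10.1.7. Nothing here bears on the screening or end-of-study scans, and the documents do not show which schedule was intended.

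**What to change.** The sponsor should choose one on-treatment schedule and make Table 5 note t, SAP Table 2 note t, 10.1.4.1 and 10.2.5 state it in the same terms, including the point from which the 6-month intervals run. Section 10.1.7 should say whether the scan continues after 12 months. Which schedule to adopt is a clinical decision for the sponsor.

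In 10.2.5, ECG should be changed to echocardiogram. In SAP 3.1, the spelled-out electrocardiogram in the MUGA item should likewise become echocardiogram, to agree with protocol 7.5 and SAP 5.8 and 5.8.5.

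The cost is wording in a protocol amendment and a SAP revision. No new analysis or table is needed, and no procedure need be added beyond what at least one current passage already requires.
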